PASS information

| | |
|--|---|
| Title | Drug utilization study of cyproterone/ethinylestradiol (Diane®-35 and generics) in the Netherlands, UK and Italy |
| Protocol version identifier | Version 7.0 |
| Date of last version of protocol | 19 March 2015 |
| EU PAS register number | EUPAS8412 |
| Active substance | Cyproterone/ethinylestradiol (CPA/EE), ATC code G03HB01, anti-androgens and oestrogens |
| Medicinal product | Diane®-35 and its generics |
| Product reference | Reference number(s) of centrally authorised products and/or, if possible, of nationally authorised products subject to the study |
| Procedure number | Referral: EMEA/H/A-107i/1357 |
| Marketing authorization holder(s) | Bayer AG on behalf of a group of MAHs |
| Joint PASS | Yes |
| Research question and objectives | 
The study objectives are to characterize new users of CPA/EE in 2011/2012 and in 2014 according to demographics, treatment characteristics, previous diagnosis of acne, hirsutism or other hyperandrogenic conditions, previous acne treatment and (concomitant) use of hormonal contraceptives. A secondary objective is to compare patient and treatment characteristics between January 1, 2011 and December 31, 2012 and January 1, 2014 and December 31, 2014.
 
An additional objective, added in 2017, is to study demographics and concomitant use of hormonal contraceptives in 2015, 2016 and 2017 as well.
 |
| Country(-ies) of study | The Netherlands, United Kingdom, Italy |
| Author | 
[name], International Research Program Manager [name], Researcher [name], PhD, Senior Research Quality Manager PHARMO Institute for Drug Outcomes Research [name]
 |

| | |
|--|---|
| | [name] [contact] |
|--|---|

Marketing authorization holder

| | |
|-----------------------------------|---|
| Marketing authorization holder(s) | Bayer AG |
| MAH contact person | [name] Global Regulatory Affairs Bayer AG [name] |

The study will be conducted in compliance with the protocol and any applicable regulatory requirements.

Throughout this document, symbols indicating proprietary names (®, TM) may not be displayed. Hence, the appearance of product names without these symbols does not imply that these names are not protected.

1. Table of contents

| | |
|---|-----------|
| 1. Table of contents | 3 |
| 2. List of abbreviations | 5 |
| 3. Responsible parties | 6 |

Research question and objectives: The study objectives are to characterize new users of CPA/EE between January 1, 2011 and December 31, 2012 and January 1, 2014 and December 31, 2014 according to demographics, treatment characteristics, previous diagnosis of acne, hirsutism or other hyperandrogenic conditions, previous acne treatment and (concomitant) use of hormonal contraceptives. A secondary objective is to compare patient and treatment characteristics between January 1, 2011 and December 31, 2012 and January 1, 2014 and December 31, 2014. [An additional objective, is to study demographics and concomitant prescription of hormonal contraceptives in 2015, 2016 and 2017 as well.](#)

Study design: A cohort study will be performed among new users of CPA/EE identified in three European population-based health care databases from the United Kingdom (UK) (THIN), the Netherlands (PHARMO) and Italy (HSD). The study will be conducted twice: the first run will include new users in 2011/2012 and the second run will include new users in 2014.

Population: The study population will include all female patients registered in the databases receiving CPA/EE in 2011 or 2012 (first run), 2014 (second run) or 2015, 2016 or 2017 (study extension) without a prescription of CPA/EE in the year prior to index date. Only patients with recorded history in the database of ≥ 365 days prior to index date will be included in the study. Patients will be followed from index date to transfer out of the database (end of follow-up available/censoring) or end of the study period.

Variables: The following characteristics will be assessed in the study population:

- Demographic characteristics (age, available history, available follow-up)
- CPA/EE treatment characteristics of the first episode of use (Diane 35 or generic, duration of CPA/EE use, prescriber)
- Acne treatment in the year prior to index date (topicals, systemic preparations and hormonal agents)
- Diagnoses in the year prior to index date (acne, alopecia, contraceptive management, menstrual problems, hirsutism, oligomenorrhoea / amenorrhoea, polycystic ovary syndrome (PCOS), seborrhea)
- Use of hormonal contraceptives before, during or after each episode of CPA/EE use (non-concomitant, potential concomitant, concomitant, no use of hormonal contraceptives). All

administration routes of hormonal contraceptives will be included in the study: pills, intra-uterine devices, implants, injections, rings and patches.

- For the study extension: demographic characteristics as above, duration of CPA/EE use and concomitant use of hormonal contraceptives

Data sources: The study will be conducted in the following databases:

- PHARMO Database Network (PHARMO) – The Netherlands
- The Health Improvement Network (THIN) – United Kingdom
- Health Search Database (HSD) – Italy

Study size: In a preliminary analysis of 2011-2012 about 9000 new users of CPA/EE were observed in the three databases.

Data analysis: Patient, treatment and diagnosis characteristics will be reported descriptively. Categorical data will be presented as counts (n) and proportions (%). Continuous data will be presented as means with standard deviation (SD) and as medians with inter quartile range (IQR) when appropriate. Prescriptions of CPA/EE and hormonal contraceptives between index date – 365 days and end of follow-up will be converted into treatment episodes of uninterrupted use. In case of an interruption between two prescriptions, use of the agent will be considered interrupted and the treatment episode ends, i.e. no gap is allowed between two prescriptions. Patients may have several treatment episodes after treatment onset. Episodes of the two classes (CPA/EE and hormonal contraceptives) may overlap, indicating concomitant drug use when there is complete overlap. Partial overlap will be defined as ‘potential concomitant use’. Results will be presented for the 2011/2012 users together and stratified by year of diagnosis.

Milestones: The data of 2014 for the three databases (THIN, PHARMO, HSD) will become available mid-2015. Considering a time period of ca. 6 months for analysis of the data and report writing, a final study report is planned for March 2016. Regulatory submission of the study protocol for the database Drug Utilization Study is planned for the third quarter of 2014. An interim report containing 2011/2012 results from the first run will be delivered in Q3 2015.

The data of 2017 for the three databases (THIN, PHARMO, HSD) will become available mid-2018. The study report for the additional objectives will be ready in Q1 2019.

5. Amendments and updates

Table 5.1 Amendments and updates to the Study Protocol

| Number | Date | Section of Study Protocol | Amendment or update | Reason |
|--------|------|---------------------------|---------------------|--------|
|--------|------|---------------------------|---------------------|--------|

Table 5.1 Amendments and updates to the Study Protocol

| Number | Date | Section of Study Protocol | Amendment or update | Reason |
|---------------|---------------|---|---|--|
| 1 | 30 March 2015 | 9.2 Setting | A prescription of CPA/EE in the year prior to index date was an exclusion criterion. In PHARMO, users were excluded as prevalent also when the prescription was more than one year prior to the index date but expired less than one year before the index date. | Exclusion of these women was more accurate. |
| 2 | 30 March 2015 | 9.2 Setting | In the Study Protocol an analysis of 2011/2012 was planned as well as an analysis of 2011 and 2012 separately. In the study report, only the calendar year analysis is presented. | The difference in recruitment periods between the analyses was confusing and the results in the analyses were similar. As the comparison of the 2014 analysis will be with the calendar years cohorts, it was decided to only present these. |
| 3 | 29 May 2015 | 9.2 Setting | PHARMO and HSD users who were new users in 2011 as well as in 2012, i.e. were using CPA/EE for a short time in 2011 and re-started after more than 365 days in 2012, were included in both populations. In THIN the 365-day period was applied before the date of study period entry, i.e. before Jan 1, 2011. By definition no users could re-enter in 2012. | At CEIFE standard procedure is to apply the medication-free period to the time before entry date rather than the index date. In practice this leads to only very small differences in numbers of users selected. |
| 4 | 29 May 2015 | 9.3 Variables | The index date was included in the assessment of diagnoses of acne and other hyperandrogenic conditions. | Extending the time window up to the index date also included the diagnoses recorded on the date of CPA/EE prescription, i.e. the likely indication of use. |
| 5 | 19 June 2015 | 9.3.2 Definition of switching and (potential) concomitant use of CPA/EE and hormonal contraceptives | In THIN, HC episodes were only created after the index date, not before. Overlap between other HC and CPA/EE before index date was assessed examining overlap between HC prescriptions and the first CPA/EE episode. | Different interpretation of the Study Protocol and different local standard programs. |

Table 5.1 Amendments and updates to the Study Protocol

| Number | Date | Section of Study Protocol | Amendment or update | Reason |
|--------|------------|---------------------------------|---|---|
| 6 | April 2017 | 8.2. Additional study objective | 
Study objectives added are to assess among new users of CPA/EE in 2015, 2016 and 2017:
 
 ○ Patient demographics ○ (Concomitant) use of hormonal contraceptives ○ To assess trends in concomitant use over 2011-2017 (excluding 2013) | 
At the beginning of December 2016, right after the PRAC December meeting, PRAC concluded that the Benefit/Risk balance of Diane-35 and its generics remains unchanged. However, it was requested that Bayer do the the following:
 
 • Submission to CA of a follow-up review of available drug utilisation data from electronic healthcare record databases* comparing the patterns of concomitant use over time (Q1 2019) • Update the RMP to include the requested follow-up review of drug utilisation data as a category 3 study, and submission to CA (June 2017). 
*The MAH is requested to use the same methodology and mode of results presentation as in the previous database DUS, for facilitating the comparison of patterns of use over time. For the same reason, use of the same databases is preferred.
 |

6. Milestones

Regulatory submission of the study protocol for the database Drug Utilization Study is planned for the third quarter of 2014. A progress (interim) report containing 2011/2012 results will be delivered in Q3 2015.

The data of 2014 for the three databases (THIN, PHARMO, HSD) will become available mid-2015. Considering a time period of ca. 6 months for analysis of the data and report writing, a final study report is expected to be available by March 2016. Separate study results for the three partner databases will be compiled in one document. Currently planned dates for deliverables are indicated in Table 6.1. The data of 2017 for the three databases (THIN, PHARMO, HSD) will become available mid-2018. The study report for the additional objectives will be ready in Q1 2019.

Table 6.1 Planned deliverables

| Deliverable | Date |
|--|-----------------------------------|
| Start of data collection | One month after protocol approval |
| End of data collection | January 2016 |
| Progress (interim) report to PRAC | Q3 2015 |
| Final report of study results | March 2016 |
| Start of data collection for additional objectives | Q3 2018 |
| End of data collection for additional objectives | Q3 2018 |
| Final report of study results | Q1 2019 |

7. Rationale and background

Cyproterone acetate (CPA) 2mg, in combination with ethinylestradiol (EE) 35mcg is a medicinal product currently indicated for the treatment of moderate to severe acne and/or for hirsutism in women of reproductive age. Androgen-dependent symptoms such as acne, hirsutism, seborrhea, and alopecia, as well as androgen sensitivity-related symptoms of Polycystic Ovary Syndrome (PCOS) have been considered as potential therapeutic targets for CPA. Due to the mode of action and the dose and regimen, the preparations also act as effective contraceptives. Market authorization was first granted in 1985.

A review of CPA/EE was triggered by the French medicines agency, the National Agency for the Safety of Medicine and Health Products (ANSM), following its decision to suspend CPA/EE in France within three months in January 2013. The French decision followed a national review of the medicine by ANSM. The Coordination Group for Mutual Recognition and Decentralised Procedures – Human (CMDh) endorsed the recommendation of the European Medicines Agency’s Pharmacovigilance Risk Assessment Committee (PRAC), which concluded that the benefits of CPA/EE (cyproterone acetate 2mg / ethinylestradiol 35mcg) outweigh the risks, provided that several measures are taken to minimize the risk of thromboembolism. These medicines should be used solely in the treatment of moderate to severe acne related to androgen sensitivity and/or hirsutism in women of reproductive age. Furthermore, CPA/EE should only be used for the treatment of acne when alternative treatments, such as topical therapy and antibiotic treatment, have failed.

Since CPA/EE also acts as a hormonal contraceptive, women should not take this medicine in combination with a hormonal contraceptive. The concomitant use of CPA/EE with a hormonal contraceptive would expose women to a higher hormonal dose and therefore potentially increase the risk of thromboembolism.

During the referral procedure, the risk of thromboembolism occurring with CPA/EE was assessed as low and well known. However, to minimize this risk, the respective MAHs were required to implement further measures in addition to updating the product information, provide educational materials to prescribers and patients highlighting the risks of thromboembolism¹ and to conduct drug utilization and post authorisation safety studies.

This document presents the protocol for a drug utilization study (DUS) on the use of CPA/EE in three European countries. The outline of the study was laid out in the EU Risk Management Plan, Version

1.3 which was finalized in the Variation Worksharing Procedure procedure number NL/H/xxxx/WS/065 on 11 May 2014.

8. Research questions and objectives

8.1 Main study objectives

The main study objectives are to assess among new users of CPA/EE:

- Patient demographics
- Treatment characteristics
- Previous diagnosis of acne, hirsutism or other hyperandrogenic conditions
- Previous acne treatment
- (Concomitant) use of hormonal contraceptives

A secondary objective is:

- to compare patient and treatment characteristics between 2011/2012 and 2014

8.2 Additional objectives

An additional study objectives added are to assess among new users of CPA/EE in 2015, 2016 and 2017:

- Patient demographics
- (Concomitant) use of hormonal contraceptives
- to assess trends in concomitant use over 2011-2017 (excluding 2013)

9. Research methods

9.1 Study design

Retrospective cohort study.

9.2 Setting

The study population will include all individuals registered in the databases receiving CPA/EE (ATC G03HB01) and Gemscript codes (85864998, 86466998, 86925998, 87351998, 90826979, 91068998, 91069998, 94832990, 94913992, 94920998, 95396990, 96577998 and 97520998) between January 1, 2011 and December 31, 2012 (study period for the first run) or January 1, 2014 and December 31, 2014 (study period for the second run). The year 2013 is not included in the identification period, as this is the year in which changes in policies and recommendations for CPA/EE usage have been implemented. The date of receiving the first prescription of CPA/EE in the study period will be defined as the index date.

The annual study periods for the 2017 extension will be between January 1 and December 31 of 2015, 2016 and 2017, respectively.

Exclusion criteria are:

- Men
- <365 days recorded history in the database prior to index date
- Use of CPA/EE in the year prior to the index date, defined by
 - a prescription of CPA/EE in the year prior to index date, or
 - a prescription of CPA/EE in the year prior to entry date (start of the study period or database entry, whichever occurred first) (THIN only, see Table 5.1 deviation #3) or
 - expiration of a prescription of CPA/EE in the year prior to index date (PHARMO only, see Table 5.1 deviation #1)

Patients will be followed from index date to transfer out of the database (end of follow-up available/censoring), end of study period, whichever occurs first. The first run will include an overall analysis (2011-2012) and an analysis by calendar year (2011 and 2012), for which separate recruitments will be performed (i.e. summing patients from the analysis by calendar year 2011 and 2012 may give a higher number than for the overall analysis). In the analysis by calendar year the end of the study period will be defined as December 31 of the year of index date (December 31, 2011, December 31, 2012).

For the 2017 study extension an analysis by calendar years will be performed..

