9.6.3 Health Search Database (HSD) - Italy

HSD contains information recorded by GPs only. Patients' demographic details are linked through the use of an encrypted code with clinical records (diagnoses, referrals, and tests results), drug prescriptions (drug name, date of filled prescription, and number of days' supply), prevention records, hospital admissions, and date of death. Free-text files are also available.

To be considered for participation in epidemiological studies, GPs should meet "up-to-standard" quality criteria pertaining to the levels of coding, prevalence of well-known diseases, mortality rates, and years of recording. The "data quality" checking is performed every semester.

Study data can be manipulated and analysed using SQL, Stata or SAS syntaxes.

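### Supply running into the year before index counts as prior CPA/EE use in PHARMO only, leaving HSD fully and THIN partly without the new-user rule that the protocol calls more accurate

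*Protocol*

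**What the plan says.** The exclusion in section 9.2 opens with a single idea, "Use of CPA/EE in the year prior to the index date, defined by", followed by three alternative tests:

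- without database restriction: "a prescription of CPA/EE in the year prior to index date, or"
- for one database: "a prescription of CPA/EE in the year prior to entry date (start of the study period or database entry, whichever occurred first) (THIN only"
- for another: "expiration of a prescription of CPA/EE in the year prior to index date (PHARMO only, see Table 5.1 deviation #1"

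Table 5.1, item 1, explains the third: "In PHARMO, users were excluded as prevalent also when the prescription was more than one year prior to the index date", provided the prescription expired within that year. The reason given is: "Exclusion of these women was more accurate". The table does not say why HSD and THIN are left out. Item 3 describes the THIN rule: "In THIN the 365-day period was applied before the date of study period entry, i.e. before Jan 1, 2011".

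The limit to PHARMO stands in the current text of section 9.2, not only in the amendment table, and no separate rule is set for 2015-2017. Section 9.3.1 gives every CPA/EE prescription a duration of 28 days times the number of packs, with no database restriction. Section 9.6.3 lists what HSD holds, including "drug prescriptions (drug name, date of filled prescription, and number of days' supply".

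**The concern.** By the duration rule of section 9.3.1, a woman whose earlier supply reaches into the year before index is on CPA/EE during part of that year. PHARMO treats her as a prevalent user. HSD treats her as a new user, because only the issue date is examined. The sponsor prefers the PHARMO rule on accuracy, and the protocol names no data obstacle to using it elsewhere.

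New use defines the whole study population. Prior acne treatment and diagnoses are read in the 365 days before index. For a re-starter admitted in this way, that window partly covers time on CPA/EE, while her earlier CPA/EE prescription was issued before the window and is not counted. She can therefore look like a starter with no prior treatment. Tables 14.1 to 14.8 set the three databases side by side, so a small part of any difference between them could come from the entry rule.

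**Working it through.** The plan gives no figure on this point to reproduce. The check is date arithmetic on the three rules.

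**Inputs.** Look-back of 365 days (section 9.2). Supply S = 28 × packs (section 9.3.1). Packs per prescription are not stated, so 1, 3 and 6 packs are assumed: S = 28, 84, 168 days. For THIN, index dates are assumed evenly spread over a one-year study period.

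**Worked case.** Issue on day -400 with S = 84: the last covered day is -400 + 84 - 1 = -317, inside the 365 days before index. PHARMO excludes her and HSD includes her.

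**Minimum time off drug, HSD.** The last prescription may lie just beyond day -365, so the gap from end of supply to index is about 365 - S:

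- 365 - 28 = 337 days
- 365 - 84 = 281 days
- 365 - 168 = 197 days

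In PHARMO it is about 365 days whatever S is. In issue-date terms, PHARMO looks back 365 + S = 393, 449 or 533 days, and HSD 365.

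**THIN, with entry date at the start of the study period (Table 5.1, item 3).** The index prescription is the first in the period, so a woman indexed d days after entry has an effective look-back of 365 + d days. A case of interest has its earlier prescription 365 + s days before index, with s from 1 to S. THIN misses it only if s > d.

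- The day -400 case has s = 35, so it is missed only for d = 0 to 34: 35/365 = 9.6% of index dates. THIN already excludes it for about 90%.
- Averaged over d and s, the share missed is [S(S + 1)/2] / (365 × S) = (S + 1)/730: 29/730 = 4%, 85/730 = 12%, 169/730 = 23%. Treating the boundary day differently does not alter these rounded values.
- With entry on 1 January 2011 and a two-year period of 731 days, the shares are (S + 1)/1462: 2%, 6%, 12%. The misses all fall within one supply length of entry, so for these pack counts 2012 starters are unaffected.
- A dated case that THIN does miss: index 1 February 2014, six packs issued 1 December 2012 (427 days earlier), supply to 17 May 2013. PHARMO excludes her; HSD and THIN include her.

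**THIN, section 9.2 read literally.** Entry is then the earlier of study-period start and database entry. With at least 365 days of history before index, database entry is never later than the start of a one-year period. Entry then means database entry, the THIN rule adds nothing, and THIN is as exposed as HSD.

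**Can the rule be applied?** A 533-day look-back needs more history than the required 365 days. In Table 15.3, HSD women with under two years of history number 18 of 495, 14 of 446 and 11 of 261 (about 3% to 4%). In Table 15.2 the THIN figures are 171 of 2,760, 219 of 2,923 and 163 of 2,341 (about 6% to 7%). The older prescription is therefore observable for nearly all women.

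**The case against.** The strongest reply has four parts.

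- **The definition is met and disclosed.** Section 9.2 says prior use is defined by the listed tests, and the abstract's base definition is the issue-date rule. A reader might infer that HSD breaches the protocol's own criterion. It does not: HSD women satisfy the operational definition, and the PHARMO extension is openly cross-referenced. What stands is that one concept has been given unequal definitions without a reason.
- **THIN is different.** A reader might infer that THIN is as exposed as HSD and holds more re-starters than PHARMO. On the entry-date rule of Table 5.1, item 3, this is wrong. For 84-day supply, THIN's look-back exceeds PHARMO's 449 days whenever d > 84, which is 280/365 = 77% of index dates. The inference holds only under the literal reading of entry date.
- **The regulator asked for the same methodology** (Table 5.1, item 6), and Annex 2 already carries 2011, 2012 and 2014 counts. This stands as a constraint on how a change is made. It does not justify the difference between databases.
- **Impact is limited.** No objective compares countries. The rule is constant within each database, so trends are little disturbed. The extension does not assess acne treatment or diagnoses, and its tables are separate by database. Cross-country reading is already limited by dispensing versus prescribing data, missing specialist prescriptions in the GP databases, and private prescribing in Italy. All of this stands and keeps the point modest.

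The remark in Table 5.1 about very small differences belongs to item 3, the THIN entry date, and cannot be borrowed for the expiry rule. Section 9.9 does concede that days' supply is often not recorded and must be estimated. Expiry dates would share that uncertainty, but so do the treatment episodes that the protocol already builds.

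**Conclusion.** The point holds for HSD without qualification. For THIN it is a minor matter confined to index dates less than one supply length after entry, unless the literal wording of section 9.2 governs. The minimum drug-free interval in HSD is shorter than in PHARMO by about the length of the last supply: 28, 84 or 168 days for the assumed 1, 3 or 6 packs.

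The number of women cannot be derived, because the protocol gives neither pack counts nor restart rates. It is probably small, since each affected woman went more than 365 days without a new prescription. For scale only, each one per cent of the HSD 2014 column is 0.01 × 261 = 2.6 women.

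The consequence is for cross-database reading of Annex 1, especially prior treatment and diagnoses. The documents do not support concluding that country differences are largely produced by the entry rule, or that the 2011-2017 trends in concomitant use are invalid. The difference should be resolved or quantified, because doing so is simple and the sponsor already prefers the stricter rule.

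**What to change.** Apply the expiry test in HSD, and in THIN for consistency: exclude a woman if a CPA/EE prescription issued before index has supply reaching into the 365 days before index. Take supply from the section 9.3.1 duration, or from recorded days' supply in HSD. Use the same rule for 2011, 2012, 2014 and 2015-2017.

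To respect the regulator's request, keep the columns under the existing rule and report beside them, as a sensitivity analysis, the cohort counts and concomitant-use proportions under the harmonised rule, with the number of women removed per database and year. This replaces an unknown with a number and leaves the existing trend series intact.

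The cost is one added selection condition in the HSD and THIN programs, a re-run of the earlier cohorts in those two databases, and slightly smaller counts. It does not by itself harmonise THIN's look-back, which would still vary with index date. Section 9.2 should also be reconciled with Table 5.1, item 3, on what entry date means.
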